Our second aim is to implement a re-versioned web-based BAI in two liver clinics and to evaluate the implementability and effectiveness of this intervention to reduce alcohol consumption in Veterans with liver disorders at three- and six-months post treatment. To achieve Aim 2, we will conduct a randomized controlled trial utilizing a hybrid (Type 1) design with patient-level clinical outcome data and formative evaluation data collected (Curran et al., 2008). Participants will be randomized to one of two treatment conditions –(a) web-based BAI plus treatment-as-usual (TAU) or (b) TAU only. We will also conduct a formative evaluation to determine the feasibility and challenges of implementing the web-based BAI into liver clinics.

Method for Randomization

We plan to use a stratified permuted block design for randomizing participants where participants are stratified by site (Palo Alto or San Francisco) and baseline severity of alcohol use (alcohol dependent, not alcohol dependent). Four randomization strata will be used: not alcohol dependent (Palo Alto), alcohol dependent (Palo Alto), not alcohol dependent (San Francisco), and alcohol dependent (San Francisco). Within each stratum, we will construct blocks of consecutive patients that vary randomly in size (either 8 or 12 participants). Each block will contain equal quantities of assignments to the two study arms arranged (permuted) in random order. A random mixture of block sizes of 8 and 12 will be used to prevent forecasting

of treatment assignments by project personnel since neither the participants nor the project staff will not be blinded to the assigned treatment condition.

Web-Based BAI Content

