6.1 Reporting

The Data Safety and Monitoring Plan will capture Serious Adverse Events (SAEs), i.e., death, hospitalization. It will also capture Adverse Events (AEs), i.e., suicidal or homicidal ideation, expression of severe distress, other serious psychiatric or medical symptoms. The Data Safety and Monitoring Plan will utilize the following categories in determining the severity of an event:

- A. Classification of Event Severity: Events will be labeled according to severity which is based on their impact on the patient. An Event will be termed 'mild' if it does not have a major impact on the patient, 'moderate' if it causes the patient some minor inconvenience, and 'severe' if it causes a substantial disruption to the patient's well-being.
- B. Event Attribution Scale: Events will be categorized according to the likelihood that they are related to the study intervention. Specifically, they will be labeled either definitely, probably, possibly, or unrelated to the study intervention.
- C. Expected Risks: This study includes no invasive procedures or medications. All changes to patients' treatment will be known to their liver care team.

We will use collected data to compare rates of SAEs between the control and intervention teams. Specifically, we will compare control and intervention serious adverse event rates and their attribution quarterly on three outcomes: Admissions for alcohol detoxification (with diagnoses), all other hospitalizations, and Deaths (with diagnosis).

In addition, we anticipate that we may encounter AEs in the following domains. These are described in greater detail below.

- (1) Breach of confidentiality associated with reporting suicidal or homicidal intent to appropriate authorities or health personnel
- (2) Severe distress as indicated by: (a) an increase of more than one standard deviation from their mean score on the PHQ-9 during follow-up assessments, (b) patient verbal report of a serious psychiatric distress at follow-up, (c) patients reporting significant distress due to the content of the self-report measures, or (d) patients reporting significant distress due to the content of the brief alcohol intervention. In each case, the research personnel will consult with the PI and Study Director to determine whether the participant's distress is significant enough to warrant an AE.

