(5) Given the study population, it is possible that participants will report other serious psychiatric or medical symptoms. Research staff will be trained to monitor significant abnormal behavior and/or report that the patient perceives him/herself to be in imminent need of medical treatment. If it is determined that the patient requires immediate care, the research staff will coordinate access to appropriate services.

Both [name] and [name] hold Ph.D.s in clinical psychology and have treated patients who have mental health and alcohol use disorders. In the event of other forms of medical care being the subject of a patient safety decision, [name] will seek the advice of Co-Investigator [name]., Chief of Hepatology at the VA Palo Alto, Co-Investigator [name]. of the San Francisco VA and/or consultant [name]. of the Palo Alto VA. All three physicians have extensive experience caring for Veterans who have liver disorders. These five project staff members will be available to consult with other project staff and/or to speak with the participant if any concerning events arise.

Triggers to action will be the participant's expression of severe distress, suicidal or homicidal ideation, and/or other serious psychiatric or medical symptoms. Research staff will be trained and prepared for situations in which a participant expresses severe distress. Specifically, all project staff will have been trained on VA's suicide risk assessment and response guidelines, including the capability of directly connecting suicidal participants to the 24-hour VA suicide hotline, as well as arranging with local psychiatry crisis management staff to assess and potentially hospitalize the patient. Subsequent to any participant's expression of severe distress, ideation, or other serious symptoms, project staff will make all reasonable attempts to re-contact the participant to monitor his or her well-being until the acute situation is resolved.

Research staff will also be trained and prepared for situations in which a participant not currently in addiction treatment reports severe alcohol misuse, e.g., a blackout, delirium tremens, alcohol-related injury). Such individuals will be protected by having project staff provide a referral to substance use disorder treatment at the VA closest to where they are residing. If the VA is rejected by the participant for any reason, project staff will utilize SAMHSA's (the federal agency within HHS that funds most non-VA substance use disorder

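### Adverse events short of hospitalisation have no planned tabulation by arm, distress counts as one only after an unmasked decision, and the mild and moderate grades overlap

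*Combined protocol and SAP*

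**What the plan says.** Section 6.1 (Reporting) names two classes of event. Serious adverse events are death and hospitalisation. For the rest, it states: "It will also capture Adverse Events (AEs), i.e., suicidal or homicidal ideation, expression of severe distress", and adds other serious psychiatric or medical symptoms.

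The comparison it commits to covers the first class only: "We will use collected data to compare rates of SAEs between the control and intervention teams". This is to be done quarterly on three outcomes: "Admissions for alcohol detoxification (with diagnoses), all other hospitalizations, and Deaths (with diagnosis").

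Five adverse event domains follow: breach of confidentiality, severe distress, suicidal ideation, homicidal ideation, and other serious symptoms. Each has steps for detection or response. None has a tabulation or comparison by arm.

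Severe distress has four triggers:
- (a) a PHQ-9 rise of more than one standard deviation from the participant's mean score;
- (b) a verbal report of serious distress at follow-up;
- (c) distress caused by the questionnaires;
- (d) distress caused by the content of the BAI.

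For all four, "the research personnel will consult with the PI and Study Director to determine whether" the distress is serious enough to be an adverse event. Suicidality likewise rests on PHQ-9 self-report combined with the staff member's interaction with the participant.

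On masking, section 5.1 (Method for Randomization) says that "neither the participants nor the project staff will not be blinded to the assigned treatment condition". The double negative is a slip. The sentence gives this as the reason for varying the block size, so it means that participants and staff know the assignment.

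On severity, section 6.1 A calls an event mild "if it does not have a major impact on the patient", moderate "if it causes the patient some minor inconvenience", and severe if it substantially disrupts well-being.

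**The concern.** The BAI asks about combat experience, sexual assault and drinking to cope with PTSD symptoms, and participants then read the feedback alone (section 5.1, Web-Based BAI Content). If it harms anyone, distress or ideation is a more likely form than admission or death. Those are the events with no planned account by arm.

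Whether a distress trigger becomes an adverse event is decided case by case by people who know the arm, with no stated threshold. A count built that way can shift in either direction with the decision-makers' expectations. Trigger (d) adds a built-in asymmetry, because a TAU participant cannot meet it.

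The stake is what can be said about safety when partners consider VA-wide use (section 2.0, Significance). Adjudicated counts alone would be weak support for a statement on distress or suicidality. The severity wording also grades some events in the wrong order.

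**Working it through.** **No figure to reproduce.** The plan states no adverse event rate, safety threshold or safety power. All event and acceptance rates below are assumptions.

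**1. What is compared by arm**

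| Event or measure | Compared by arm? | Passes the adverse event decision first? |
|---|---|---|
| Detoxification admission, other hospitalisation, death | Yes, quarterly (6.1) | No such step stated |
| Severe distress as an adverse event | Not planned | Yes |
| Suicidal ideation | Not planned | Staff judgement is part of the determination |
| PHQ-9, BSI, SIP scores | Yes, as secondary outcomes (5.5, 5.6) | No |

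**2. Effect of the decision step, if adjudicated events were set side by side.** Recorded ratio = (true BAI rate × share accepted in BAI) / (true TAU rate × share accepted in TAU). Take true rates of 20% in BAI and 10% in TAU:
- 80% accepted in both: 16% / 8% = 2.0, so equal filtering leaves the ratio alone.
- 60% in BAI, 80% in TAU: 12% / 8% = 1.5.
- 40% in BAI, 80% in TAU: 8% / 8% = 1.0, and the doubling disappears.

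**3. Effect of trigger (d) alone.** Let both arms have rate c on triggers (a) to (c), and let a share d of the BAI arm independently meet trigger (d). The apparent ratio is [c + d(1 − c)] / c.
- c = 10%, d = 2%: 11.8% / 10% = 1.18.
- c = 5%, d = 5%: 9.75% / 5% = 1.95.

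This pushes the count up in BAI, while step 2 pushed it down. The net direction is unknown.

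**4. What the score comparisons can see.** With 170 per arm and 20% attrition (section 5.6), 170 × 0.8 = 136 per arm remain at six months. In a simple two-sample comparison, the standardised difference detectable with 80% power at two-sided 0.05 is (1.96 + 0.84) × √(2/136) = 0.34. If an extra 10% of the BAI arm rose by one SD, the mean would move by 0.10 × 1 = 0.10 SD. Those participants would need an average rise of 0.34/0.10 = 3.4 SD to move the mean that far. A general shift would show, but a cluster of bad cases could be missed.

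**5. Power of a comparison of event rates.** At 136 per arm, two-sided 0.05, power is about 0.64 for 10% against 20% and 0.35 for 5% against 10%. A table by arm is therefore descriptive.

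**6. How often the PHQ-9 trigger fires by chance.** The text does not say whose mean and SD are meant. Assume the between-person SD, normal scores, no true change, and the correlation of 0.5 between repeated measures from section 5.6. The change then has SD √[2(1 − 0.5)] = 1.0 of that SD, and P(Z > 1) = 0.159, about 16% per follow-up. Over two follow-ups, with all three scores equally correlated, it is about 25%, or 43 of 170 with no attrition. For correlations from 0.7 to 0.3 the two-visit figure runs from about 17% to 31%.

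**7. Severity grades.** A minor inconvenience is not a major impact, so it meets both *mild* and *moderate*. An event worse than a minor inconvenience, but neither a major impact nor a substantial disruption, meets only *mild*. The worse event gets the lower grade.

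**The case against.** The strongest reply is that much of this harm would be visible anyway. Hypothesis H2 includes psychological distress. PHQ-9, BSI, SIP and SF-12 are compared by arm, and no adverse event decision removes a score from those analyses. Mental health and substance use care, including detoxification, comes from administrative files over 12 months (sections 5.5 and 5.6, Aim 3). PHQ-9 scores, including self-reported ideation, stay in the data whatever staff decide. This stands. A reader might infer that harm short of hospitalisation cannot be seen in this trial, and the documents do not support that. The limits are that the scores are self-reported by unmasked participants to unmasked interviewers, that means can hide a few severe cases, and that no arm comparison of ideation is planned.

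Second, a reader might infer that the plan expects all five domains to result from the BAI. It does not. It says such events may be encountered in participants, and ties only trigger (d) to the BAI.

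Third, the decision step biases no analysis the plan makes, because adverse events are not compared. That is right. The ratios in step 2 are not errors in a planned result. They show why the table should include counts taken before adjudication.

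Fourth, the decision step has a purpose. Step 6 shows that counting every PHQ-9 trigger as an adverse event would fill the log with fluctuation. This also stands and shapes the fix.

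Finally, section 6.1 provides a referral when a participant not in addiction treatment "reports severe alcohol misuse, e.g., a blackout, delirium tremens, alcohol-related injury". A reader might infer that these events go unrecorded. They plausibly fall under other serious psychiatric or medical symptoms, and any admission is a serious adverse event, so I do not press it.

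**Conclusion.** The point holds in limited form, and section 6.1 should be changed. Three things rest on its text, read with the masking statement in 5.1:
- Adverse events short of hospitalisation have no planned tabulation by arm.
- Distress triggers become adverse events only by unmasked, case-by-case decision, with one trigger possible in one arm only.
- The mild and moderate grades overlap and are out of order.

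The supplied text names no masked or independent adjudicator.

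The size of any distortion cannot be derived from the documents. Under the assumptions shown, a true ratio of 2.0 could appear as 1.5 or 1.0, and trigger (d) alone could produce an apparent ratio of 1.18 to 1.95 where none exists. No planned efficacy estimate or test is affected. The gap is in safety reporting: suicidal ideation is not set out by arm, and severe distress can be judged only through mean scores or through counts that have passed an open-label filter.

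**What to change.** In section 6.1:

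1. Log every listed trigger in both arms, with date and type, before any adjudication. Record the adverse event decision in a separate field, so that a trigger is not automatically an adverse event and a discounted trigger stays on file. State whose mean and whose SD the PHQ-9 trigger uses.
2. Add one descriptive table, quarterly and final, of participants with at least one trigger and participants with at least one adjudicated adverse event, by domain and arm. Show trigger (d) on its own line. Make no claim of power.
3. Reconcile the severity definitions so that the three grades are ordered and mutually exclusive.

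This alters recording and reporting only. How staff respond to a participant in distress is untouched, and no new data or staff are needed. The costs are protocol wording, one more table, and a longer log. Much of the added length may be PHQ-9 rises due to chance, roughly 16% of participants per follow-up under the assumptions in step 6, which is why the two fields should stay separate.

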7.0 Privacy and Confidentiality

We will use Protected Health Information (PHI) for this study only. PHI will not be disclosed to anyone outside of the PI, VA Palo Alto and VA San Francisco Co-Is, and research team members involved with data collection and management.

All PHI and final data collected for this study will be managed and housed at the Center for Health Care Evaluation (CHCE), located on the VA Palo Alto campus (in Menlo Park). Regarding computers and relevant technology, the CHCE has the following: a centralized server and mass data storage device that is fire-walled, encrypted, and backed-up daily; two information technology specialists to ensure data security and integrity; networked personal computers for all personnel; and statistical, publishing and database software for data management and analysis. Relevant to data storage and safety, CHCE has access to local Windows Active Directory Domain Controllers, a UNIX NIS Server and Network Appliance storage facilities. These resources allow large amounts of research data to be stored and analyzed within a secure environment, while still connected to VA computing resources. Network infrastructure and connectivity are maintained by the Shared Computer and Resources Facility (SCARF) that serves CHCE and the VA's Cooperative Studies Program Coordinating Center (CSPCC), HERC, and the Program Evaluation and Resource Center.

All PHI and related data collected for this study will be managed and housed using standard CHCE protocols for housing such data. For example, all paper and hard copy records will be kept in a locked cabinet in a locked room in building 324. Only authorized research staff will have the key to the locked cabinet. All electronic records will be kept on maintained, encrypted VA servers housed in building 324. All files and folders will be password protected. The ISO/PO will be notified within one hour if data loss or misuse is discovered.

8.0 Communication Plan

The research team will regularly meet to discuss the study's progress and address any adverse events or unanticipated issues. The study coordinators at VAPAHCS and SFVAMC will be in continuous communication as they coordinate screening and data collection and management. Both will also be in direct communication with the PI [name] and Co-PI [name] to remain up to date on the study protocol and to ensure that any serious adverse events or unanticipated problems are reviewed and documented appropriately. Both the PI and Co-PI ([name]) will provide training to study staff in consent form procedures and will work with both sites to inform them of updates to the study.

